^f **For women of childbearing potential only (defined in Criterion 215 in Section 4.2).**

^g AMG 510 will be administered daily on a repeated basis with no planned off treatment days. AMG 510 must be administered in the fasted state (no food or liquids, except water, 2 hours before to 1 hour after dosing).

^h Radiological imaging and tumor assessments are required at screening and every 6 ± 1 weeks. After **four** 6-week response assessments, radiological imaging and tumor assessment frequency will be performed every 12 ± 1 weeks until disease progression, start of new anti-cancer treatment, death, or withdrawal of consent until end of study. MRI/CT scans can be obtained earlier if clinical deterioration necessitates an earlier scan at the discretion of the managing physician. End of treatment CT/MRI should be performed only for subjects that discontinue treatment for a reason other than disease progression per **RECIST 1.1** criteria. Every assessment must include the chest, abdomen, pelvis, and all other known sites of disease. Tumor burden assessments will be performed based on **RECIST 1.1** guidelines ([Appendix D](#)). Radiographic response (CR and PR) requires confirmation by a repeat consecutive assessment 4 weeks after the first detection of response.

ⁱ All subjects with history of brain metastasis must have MRI of the brain performed within 28 days prior to enrollment. Only if MRI is contraindicated, then CT with contrast is acceptable. Subsequently, MRI brain scans can be performed at any time if clinically indicated or per standard of care. Any additional imaging used to evaluate or determine response (eg, PET, CT/PET, bone scan, etc) should be sent along with the required imaging to the central imaging vendor promptly upon completion.

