7.5 Radiological Imaging Assessment

The extent of disease will be evaluated by contrast-enhanced MRI/CT according to **RECIST 1.1** ([Appendix D](#)). All radiological imaging will be performed as indicated in the Site Imaging Manual provided by the central imaging core laboratory. In order to reduce radiation exposure for subjects, low dose CT should be utilized whenever possible.

The screening scans must be performed within 28 days prior to enrollment and will be used as baseline. All subsequent scans will be performed in the same manner as at screening, with the same contrast, preferably on the same scanner. Radiological assessment must include MRI/CT of the chest, abdomen and pelvis, as well as assessment of all other known sites of disease as detailed within the Site Imaging Manual. Magnetic resonance imaging (MRI) of the brain should be performed if signs or symptoms suggestive of central nervous system metastases are present.

The same imaging modality, MRI field strength and intravenous and oral contrast agents should be used at screening should be used for all subsequent assessments. Liver specific MRI contrast agents should not be used. To reduce potential safety concerns,

macrocyclic gadolinium contrast agents are recommended per National Health Institute guidelines, or follow local standards if more rigorous.

During treatment and follow-up radiological imaging of the chest, abdomen, pelvis, as well as all other known sites of disease, will be performed independent of treatment cycle every 6 ± 1 weeks for the first 4 response assessments. After **four** 6-week response assessments, radiological imaging and tumor assessment will be performed every 12 ± 1 weeks. Radiologic imaging and tumor assessment will be performed until disease progression, start of new anticancer treatment, death, withdrawal of consent or until end of study. Imaging may also be performed more frequently if clinically necessitated at the discretion of the managing physician. Radiographic response (complete response, partial response) requires confirmation by a repeat, consecutive scan at least 4 weeks after the first documentation of response and may be delayed until the next scheduled scan to avoid unnecessary procedures.

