Overall Response: Confirmation of Complete Response (CR) and Partial Response (PR) required

Overall Response First Time Point	Overall Response Second Time Point	Best Overall Response
CR	CR	CR
CR	PR	SD, PD or PR [†]
CR	SD	SD provided minimum criteria for SD duration met, otherwise, PD
CR	PD	SD provided minimum criteria for SD duration met, otherwise, PD
CR	NE	SD provided minimum criteria for SD duration met, otherwise, NE
PR	CR	PR
PR	PR	PR
PR	SD	SD
PR	PD	SD provided minimum criteria for SD duration met, otherwise, PD
PR	NE	SD provided minimum criteria for SD duration met, otherwise, NE
NE	NE	NE

[†] If a CR is truly met at first time point, then any disease at a subsequent time point, even disease meeting PR criteria relative to baseline, makes the disease PD at that point (since disease must have reappeared after CR). Best response would depend on whether minimum duration for SD was met. However, sometimes “CR” may be claimed when subsequent scans suggest small lesions were likely still present and in fact the subject had PR, not CR at the first time point. Under these circumstances, the original CR should be changed to PR and the best response is PR.

Special Notes on Response Assessment

- Nodal lesions – Lymph nodes identified as target lesions should always have the actual short axis measurement recorded, even if the nodes regress to below 10 mm on study. In order to qualify for CR, each node must achieve a short axis < 10 mm, NOT total disappearance. Nodal target lesion short axis measurements are added together with target lesion’ longest diameter measurements to create the sum of target lesion diameters for a particular assessment (timepoint).
- Target lesions that become “too small to measure” – While on study, all lesions (nodal and non-nodal) recorded at baseline should have their measurements recorded at each subsequent evaluation. If a lesion becomes less than 5 mm, the accuracy of the measurement becomes reduced. Therefore, lesions less than 5 mm are considered as being “too small to measure”, and are not measured. With this designation, they are assigned a default measurement of 5mm. No lesion measurement less than 5mm should be recorded, unless a lesion totally disappears and “0” can be recorded for the measurement.

Approved

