Baseline ECG Values in Triplicate:

The mean of the three triplicate ECG results should be calculated for Baseline. If fewer than three triplicate ECG results are available, the mean of available triplicate should be calculated. For all post-baseline ECG, the mean of one triplicate ECG results at the same assessment will be calculated and used in the analysis.

When an ECG is missing within a triplicate, all available data will be averaged for that time point.

Best Overall Response (BOR):

Best overall response (BOR) for a subject is the best observed disease response per RECIST v1.1. Overall response assessments occurring after the start of the first subsequent anticancer therapy will not be included. No additional derivations will be required to classify the response.

BOR is defined as the best response in the following order: CR, PR, SD, PD, or NE, where CR and PR require confirmation by a repeat, consecutive scan at least 4 weeks after the first documentation of response. A best overall response of SD requires an on-study imaging of SD or better no earlier than 6 weeks after cycle 1 day 1; otherwise the best overall response will be not evaluable (NE)

Please refer Protocol Appendix D for more details.

Body Mass Index (BMI):

Body Mass Index should be calculated using the following formula:

$$\text{BMI (kg/m}^2\text{)} = \text{weight (kg)} / [\text{height (cm)} / 100]^2$$

Body Surface Area (BSA):

The Body Surface Area should be calculated using the following formula:

$$\text{BSA} = 0.007184 \times \text{weight(kg)}^{0.425} \times \text{height(cm)}^{0.725}$$

Change from Baseline:

Change from Baseline is the arithmetic difference between post-dose assessments and Baseline value.

Change (absolute) from Baseline = (Post-baseline Value – Baseline Value)

Change (percent) from Baseline = [(Post-baseline Value – Baseline Value) /
Baseline Value] x 100

Dose Limiting Toxicity (DLT):

Dose-limiting toxicity (DLT) is defined as AMG 510-related toxicity with an onset within the first 21 days following first dose with the criteria defined in section 6.1.1.2.1 of the Protocol.

Disease control rate (DCR):

DCR is defined as the proportion of patients in whom the best overall response is determined as complete response (CR), partial response (PR) or stable disease (SD) > 6 weeks.

Duration of response (DOR):

The duration of response is defined as time from first evidence of PR or CR to disease progression or death due to any cause.

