9.5.2 Analyses of Secondary Efficacy Endpoint(s)

DOR will be calculated only for subjects who achieve a best overall response of PR or better. Subjects will be censored following the censoring strategy described in the definition of PFS time in [Table 1](#). The distribution of DOR, including the median and quartiles will be characterized using the Kaplan-Meier(KM) method based on the subjects who achieve a best response of PR or better. The 95% CIs for the median and

quartiles of PFS will be constructed using the method of [Klein and Moeschberger \(1997\)](#) with log-log transformation. The rates for select durations (eg, > 3, > 6, > 9, > 12 months) will be reported. The 95% CIs for PFS rates will be estimated using the methods by [Kalbfleisch and Prentice \(1980\)](#) with log-log transformation. KM curve can be done for DOR if at least 10 subjects have a CR/PR.

The proportion of subjects with disease control (CR, PR or SD > 6 weeks) with corresponding exact 95% CI will be calculated using the Clopper-Pearson method.

Duration of Stable Disease will be analyzed using the same method as describe for DOR.

The distribution of PFS, including median, will be estimated using the Kaplan-Meier method. PFS rate at the selected time points (6 months and 12 months) will be reported. The 95% CIs for the median and other percentiles of PFS will be constructed using the method of [Klein and Moeschberger \(1997\)](#) with log-log transformation. The 95% CIs for PFS rates will be estimated using the methods by [Kalbfleisch and Prentice \(1980\)](#) with log-log transformation.

OS will be analyzed using the same method as describe for the PFS endpoints.

Time to response will be summarized with the non-missing sample size (n), mean, standard deviation, median, minimum, and maximum for responders, ie, subjects who achieve best overall response of sCR, CR, BGPR, or PR.

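### The SAP's 6-week minimum for stable disease falls inside the protocol's 5-to-7-week window for the first scan, so some compliant subjects are classed NE and lost from disease control

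*Supplement*

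**What the plan says.** SAP v2.0, Section 5, Best Overall Response, allows SD as the best response only with on-study imaging of "SD or better no earlier than 6 weeks after cycle 1 day 1". A subject who does not meet this is NE. The same definition orders responses as CR, PR, SD, PD, NE and sends the reader to protocol Appendix D for detail.

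SAP Section 5, Disease control rate, counts complete response, "partial response (PR) or stable disease (SD) > 6 weeks". SAP 9.5.2 repeats the strict inequality.

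Protocol (Amendment 3), Table 6 footnote h: "Radiological imaging and tumor assessments are required at screening and every 6 ± 1 weeks". Section 7.5 gives the same interval, "treatment cycle every 6 ± 1 weeks for the first 4 response assessments", and ties it to calendar time rather than to treatment cycle.

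Protocol Appendix D refers to a minimum SD duration but never states a number. For some response sequences, including PR followed by PD, its entry is "SD provided minimum criteria for SD duration met, otherwise, PD". For PR followed by NE, failure of the minimum gives NE. The protocol's own DCR definition (Section 10.1.1.2.2) carries no SD minimum.

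**The concern.** A timing rule for SD should not reject a scan that the protocol regards as on time. Here the floor is the midpoint of the permitted window, and no passage makes an allowance for the window. Whether a subject with one SD scan counts as having disease control can then depend on clinic scheduling rather than on disease. The floor can only remove subjects from disease control, so the bias in DCR is downward.

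Two drafting problems add to this. BOR accepts exactly 6 weeks and DCR asks for more than 6 weeks, so two programmers could derive different DCRs from the same data. The instruction to assign NE can also put a subject with documented progression in the NE row of the BOR table. DCR is a secondary endpoint in both phases.

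**Working it through.** The plan states no assumed rate or precision for DCR, so there is no figure of its own to reproduce. The check is a day count followed by an illustration.

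**Step 1: the window.** 6 ± 1 weeks = 42 ± 7 days = days 35 to 49 after C1D1, which is 15 days.

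**Step 2: each in-window day against each rule.** The SAP's study-day formula adds 1 to elapsed days, so a scan 42 days after C1D1 is study day 43.

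| Rule | How 6 weeks is counted | In-window days that fail | Share of window days |
|---|---|---|---|
| BOR, at least 6 weeks | elapsed days ≥ 42 | 35-41 | 7/15 = 47% |
| BOR, at least 6 weeks | study day ≥ 42 | 35-40 | 6/15 = 40% |
| DCR, more than 6 weeks | elapsed days > 42 | 35-42 | 8/15 = 53% |
| DCR, more than 6 weeks | study day > 42 | 35-41 | 7/15 = 47% |
| Proposed, at least 5 weeks | elapsed days ≥ 35 | none | 0/15 |

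These are shares of calendar days, not of scans.

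**Step 3: the nominal day.** A scan on elapsed day 42 passes BOR. It fails DCR on elapsed days and passes on study days. It also passes if SD of more than 6 weeks refers to the SAP's duration of stable disease, which runs from start of treatment to progression or death: SD on day 42 with progression at about week 12 is then long enough. The SAP does not choose between these. The duration reading does not rescue a day 35-41 scan, because the DCR definition is built on BOR, which is already NE.

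**Step 4: who is affected.** All of the following must hold: the only SD or unconfirmed-response scan is before day 42; it is followed by PD, death or no later evaluable scan; and there is no confirmed CR or PR.

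**Step 5: NE or PD.** Take PR on day 38, then PD at the next scan. The response ordering gives PD, Appendix D gives PD, and the SAP's SD sentence gives NE. Neither category is disease control, so this changes the BOR table and leaves DCR alone.

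**Step 6: illustrative loss.** DCR loss = s × w. Here s is the share of subjects whose only SD or unconfirmed-response scan is the first one, and w is the share of first scans before 6 weeks. Both are assumed, and the product treats them as independent.

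- Low: 0.10 × 0.10 = 1 point.
- Middle: 0.20 × 0.25 = 5 points, about 5 of 105 NSCLC or 3 of 60 CRC subjects.
- High: 0.30 × 0.50 = 15 points, about 16 of 105 or 9 of 60.

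The 105 and 60 are the planned evaluable numbers for ORR, used only for scale.

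**The case against.** The case on the other side is substantial and limits the point.

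- A reader might infer that any early first scan turns SD into NE. It does not. BOR uses all assessments and scans continue every 6 weeks, so one later SD-or-better scan restores SD.
- Subjects who stop treatment without progression should have an end-of-treatment scan (Section 7.5; visit within 14 days of last dose, Section 7.2.3) and then scans every 12 weeks in follow-up (Section 7.2.5). Many will therefore obtain a qualifying scan. This leaves mainly those who progress at the next assessment, die, or have no evaluable scan before withdrawal or new therapy.
- A reader might infer that a nominal-day scan is excluded from DCR. Step 3 shows that this depends on the reading. It is an ambiguity.
- A reader might infer a general conflict with Appendix D. Its rows that assign PD cover CR followed by SD or PD, and PR followed by PD. There is no row for SD followed by PD, and PR followed by NE agrees with the SAP.
- The phase 1 table in protocol Section 2.6.2.1 shows 8 SD among 10 six-week scans, but that does not give s. Of those 8, 4 were SD again at week 12, 1 was NE and 3 had no entry. Discontinuations for progression at 62 and 72 days, among 22 subjects, show that the pattern can occur, not how often.
- Appendix D leaves the minimum open, so the SAP is entitled to supply one, and 6 weeks is a conservative choice.

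What stands is that the chosen number contradicts the protocol's scan window, and that the SAP's two thresholds differ.

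**Conclusion.** The point holds in a limited form. Applied as written, the SAP classes as NE, and drops from DCR, a subject whose only SD or unconfirmed-response scan was compliant but fell on days 35-41 and was followed by PD, death or no later evaluable scan. The direction is downward. The size is unknown: about 1 to 15 points under the assumed ranges, neither of which has a source in the documents, so the upper end should not be read as an expected loss.

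The mismatch between BOR and DCR at exactly 6 weeks is a real inconsistency of uncertain effect. The NE-versus-PD wording affects the BOR table only. It would be wrong to extend the point to the primary endpoint: confirmed CR and PR have no 6-week floor, and the benchmarks and sample sizes concern ORR alone. The change is worth making before the data are analysed, but it does not threaten the trial's main conclusion.

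**What to change.** Set one SD minimum at the lower edge of the scan window: an assessment of SD or better at least 5 weeks, that is 35 elapsed days, after C1D1. Use identical wording in the BOR definition, the DCR definition and SAP 9.5.2. State that it refers to scan timing and is counted as scan date minus C1D1 date (study day 36 or later under the SAP's formula). Where the minimum is not met and the next assessment is PD, assign PD; keep NE only when there is no later evaluable scan.

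The cost is SAP wording and one derivation constant, with no new data. The downside is a slightly less strict definition of SD.

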7.2.15 Electrocardiograms (ECGs)

Subject must be in supine position in a rested and calm state for at least 10 minutes before ECG assessment is conducted. If the subject is unable to be in the supine position, the subject should be in most recumbent position as possible. ECGs should be performed in a standardized method, in triplicate, and run consecutively, prior to blood draws or other invasive procedures. Each ECG must include the following measurements: QRS, QT, QTc, RR, and PR intervals.

- ≥ 3 baseline ECGs collected **at least** ≥ 30 **seconds** apart, with each baseline ECG in triplicate run consecutively (ie, total ≥ 9 ECGs)
- Triplicate ECGs at time points after dosing

Baseline is defined as prior to dosing on cycle 1 day 1. The PI or central reader will review all ECGs. ECGs will be transferred electronically to an ECG central reader for analysis per Amgen instructions. Once signed, the original ECG tracing will be retained with the subject's source documents. At the request of the sponsor, a copy of the original ECG will be made available to Amgen. Standard ECG machines should be used for all study-related ECG requirements. In certain circumstances Amgen may be able to provide a standard ECG machine if a site is unable to provide one.

For phase 2, intense ECG collection will be performed at select sites in up to approximately 30 subjects at time points described for Group A. Sparse ECG collection will be performed in the remaining subjects at time points described for Group B.

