The duration of complete response is defined as time from the first evidence of CR to disease progression or death due to any cause.

DOR will be calculated only for subjects who achieve a confirmed best overall response of PR or better.

Subjects will be censored following the censoring strategy described in the definition of PFS time in [Table 1](#).

Duration of stable disease:

Duration of stable disease will be measured from the start of treatment to disease progression or death due to any cause.

Subjects will be censored following the censoring strategy described in the definition of the PFS time in [Table 1](#).

End of IP administration (End of IP Admin):

End of IP Admin for each subject is defined as the date the decision was made to end IP as recorded on the End of Investigational Product Administration CRF page.

End of Study (Individual Subject):

End of study for each subject is defined as the date the subject last completed a protocol-specified procedure. The date will be recorded on the End of Study CRF page.

End of Study (Primary Completion):

It is defined as when the last subject is assessed or receives an intervention for the purposes of final collection of data for the primary endpoint(s), whether the study was conducted as planned in the protocol or was terminated early.

End of Study (End of Trial):

The end of study date is defined as the date when the last subject across all sites is assessed or receives an intervention for evaluation in the study (ie, last subject last visit), following any additional parts in the study (eg, long-term follow-up), as applicable.

Fridericia-corrected QT Interval (QTcF):

The Fridericia correction will be calculated from the investigator reported QT (msec) and RR interval (msec), as follows:

$$QTcF=QT/(RR/1000)^{1/3}$$

Investigational Product:

The term 'investigational product' is used in reference to AMG 510.

[REDACTED]

Last Investigational Product Dose Date:

The last IP date for each subject is defined as the latest date IP administered.

Long Term Follow-Up:

Following the SFU visit, there will be a LTFU period during which data will be collected on the subjects' health condition, disease status, survival and subsequent anticancer treatment.

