9.6.6 Electrocardiogram

Summaries over time and/or changes from baseline over time will be provided for all ECG parameters.

Subjects' maximum change from baseline in QT interval corrected by Fridericia's formula will be categorized and the number and percentage of subjects in each group will be summarized. Unscheduled assessments will be included in the determination of the maximum change. The categories are ≤ 30 msec, $> 30 - 60$ msec, > 60 msec.

Subjects' maximum post baseline values will also be categorized and the number and percentage of subjects in each group will be summarized. The categories are ≤ 450 msec, $> 450 - 480$ msec, $> 480 - 500$ msec, > 500 msec.

All on-study ECG data will be presented and select parameters of interest may be plotted.

In addition, the relationship between AMG 510 exposure and change from baseline in QTc will be explored graphically. More details on analyses of ECG data are available in Supplemental Statistical Analysis Plan for ECGs Analyses.

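### The SAP derives QTcF from site-reported QT and RR although the protocol sends ECGs to a central reader, and no rule says which value takes precedence

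*Supplement*

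**What the plan says.** SAP Amendment 1, section 5 (Definitions, Fridericia-corrected QT Interval): "The Fridericia correction will be calculated from the investigator reported QT (msec", together with the investigator-reported RR interval, followed by the usual formula.

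SAP section 5 (Baseline ECG Values in Triplicate) averages three triplicates at baseline. After baseline, "For all post-baseline ECG, the mean of one triplicate ECG results at the same assessment will be calculated and used in the analysis".

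SAP 9.6.6: "Subjects' maximum change from baseline in QT interval corrected by Fridericia's formula will be categorized". The change categories are up to 30, above 30 to 60, and above 60 msec. Maximum post-baseline values are categorised as well. The section also plans a graphical look at exposure against QTc change and refers to a supplemental ECG analysis plan, which is not shown, for more detail.

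Protocol Amendment 3, section 7.2.15: "ECGs will be transferred electronically to an ECG central reader for analysis per Amgen instructions". The sentence before it reads: "The PI or central reader will review all ECGs".

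The main SAP does not mention the central ECG reading. SAP section 10 lists only PFS2 as a change from the protocol's analyses.

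**The concern.** The protocol arranges a standardised reading of the ECGs, and the SAP then computes its QTcF from the other source. The wording in SAP section 5 is the same as in SAP version 1.0, which was written for protocol Amendment 1; that protocol, as shown, mentions no central ECG reader. When the SAP was amended, the neighbouring baseline rule was updated to three triplicates, in line with protocol 7.2.15. The QTcF source was not touched, so it looks like a carry-over.

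Two things are at stake. First, if site and central values both exist and differ, the main SAP gives no rule for choosing, and the supplemental plan could end up reporting a second set of QTcF values. Second, the tabulated quantity is a maximum per subject. Independent reading error does not average out of a maximum: it raises it, and can move subjects into a higher category with no drug effect. ECG changes belong to the phase 1 primary safety endpoint.

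**Working it through.** The plan states no figure that depends on the QTcF source, so there is nothing to reproduce. The check has two parts: a comparison of the texts, and an illustration of how much the choice could matter.

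**Texts side by side**

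- Protocol 7.2.15: ECGs go to a central reader for analysis.
- SAP section 5: QTcF uses investigator-reported QT and RR.
- SAP 9.6.6: the QTcF category tables rest on the SAP section 5 derivation.
- None of these gives a precedence rule.

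**Inputs for the illustration**

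- Baseline is the mean of three triplicates and each post-baseline value is one triplicate mean (SAP section 5).
- Category limits are 30 and 60 ms (SAP 9.6.6).
- Intensive sampling is taken as 14 post-dose time points (assumed; protocol Table 5 shows about 16 in cycle 1 for phase 2 Group A).
- Sparse sampling is taken as three post-baseline time points (about what protocol Tables 5 and 6 show for Group B; the columns are imperfect in the extracted text). Up to approximately 30 phase 2 subjects are in Group A, so about 200 − 30 = 170 would be in Group B.
- Assumed, because the documents give no SD: central triplicate-mean SD 4 ms; extra site-reading SD e of 5 to 10 ms on each triplicate mean; errors independent and normal; no drug effect.

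**Step 1. SD of one triplicate mean, s = √(4² + e²)**

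- Central: 4.0 ms
- e = 5: √41 = 6.4 ms
- e = 10: √116 = 10.8 ms

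**Step 2. SD of a single change from baseline**

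The baseline averages three triplicates, so its variance is s²/3, and SD(change) = s × √(1 + 1/3) = 1.155 s.

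- Central: 4.6 ms
- e = 5: 7.4 ms
- e = 10: 12.4 ms

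**Step 3. Expected maximum change**

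Baseline error has mean zero, so the expected maximum change is s times the expected maximum of K standard normal values: 1.70 for K = 14 and 0.85 for K = 3.

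| | Central | e = 5 | e = 10 | Rise |
|---|---|---|---|---|
| 14 time points | 6.8 ms | 10.9 ms | 18.3 ms | about 4 to 12 ms |
| 3 time points | 3.4 ms | 5.4 ms | 9.1 ms | about 2 to 6 ms |

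**Step 4. Chance that the maximum change exceeds a category limit**

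Given baseline error b, with SD s/√3, the chance of exceeding c is 1 − Φ((c + b)/s)^K, averaged over b.

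| | Central | e = 5 | e = 10 |
|---|---|---|---|
| >30 ms, 14 time points | about 0% | 0.03% | 9% |
| >30 ms, 3 time points | about 0% | under 0.01% | 2% |
| >60 ms, either | about 0% | about 0% | about 0.001% or less |

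A visible effect on the category table therefore needs site-reading error near the upper end of the assumed range, and it falls on the >30 ms category only.

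**The case against.** The strongest reply is that nothing in the documents says site readings are less precise. That stands: there is no SD and no agreement study, so the direction of the effect is a reasoned expectation and its size is assumed.

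Four further readings are tempting and should be resisted.

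- *That every ECG is read centrally.* The transfer sentence refers to ECGs under the sponsor's instructions, which are not shown, and the review sentence says the PI or the central reader. Complete central coverage is not established.
- *That differences between about 100 sites add error to each change.* A constant site, reader or machine offset cancels in a within-subject change. Only inconsistency within the same subject adds error to it. An offset would not cancel in the table of maximum post-baseline values.
- *That the exposure-QTc secondary endpoint is blurred.* In SAP 9.6.6 that analysis is followed at once by the reference to the supplemental ECG plan, which may specify central readings.
- *That the maximum shifts by 4 to 12 ms in most subjects.* That range belongs to intensive sampling; with sparse sampling it is about 2 to 6 ms.

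It is also true that these are descriptive summaries, and that no test, stopping rule or sample size in the documents depends on the QTcF source. But the reference to the supplemental plan does not remove the point. The main SAP itself fixes both the QTcF inputs and the category tables.

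**Conclusion.** The mismatch is real in the latest protocol and SAP. The main SAP ties its QTcF category tables to site-reported intervals, the protocol provides for central reading, and no precedence rule is given in the documents shown. Using the central reading is a specific improvement that should be made.

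The likely consequence is modest. Under the stated assumptions, the SD of a single change rises from 4.6 to between 7.4 and 12.4 ms, the >30 ms category is inflated noticeably only near 10 ms of extra error, and the >60 ms category hardly moves. These figures depend on assumed SDs, independent errors and no drug effect; errors correlated across a subject's time points would change them. Whether the exposure-QTc analysis is affected cannot be judged without the supplemental ECG plan.

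**What to change.** In SAP section 5, state that QTcF is computed from the central reader's QT and RR. Use the investigator's value only where no central reading exists, and flag those records in the listings and tables. Put the same source and precedence rule in the supplemental ECG plan, so that the category tables and the exposure-QTc analysis rest on the same data.

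The text change is a sentence or two. The practical cost is transferring the central ECG data into the analysis database and reconciling them with it: SAP 8.2 describes data supplied by the sponsor's data management group and the RAVE database, and mentions no central ECG transfer.
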